APPENDIX A -- METHACETIN BREATH TEST PARAMETERS

The BreathID MCS System measures the change of the $^{13}\text{CO}_2/^{12}\text{CO}_2$ ratio in exhaled breath following ingestion of ^{13}C -Methacetin compared to the $^{13}\text{CO}_2/^{12}\text{CO}_2$ ratio before ingestion. This measure is called 'Delta Over Baseline' (DOB) and is automatically measured every 2-3 minutes, resulting in approximately 23 DOB's and corresponding time points over one hour. Subjects visit height and weight as well as all available DOB measures with corresponding time point (T) will be retrieved from the completed eCRFs.

1. DOB values must be sorted by time before any calculation, while a first pair of data points should always be added with time $T_0=0$ min and $DOB_0=0$.
2. The DOBs will be transformed into percentage dose recovery rates (PDRs) by normalizing the DOB using patient body weight and height at each observed time point (i) by using the following formula:

$$PDR_i = 0.01817853 \cdot DOB_i \cdot Weight^{0.5378} \cdot Height^{0.3963}$$

While Weight is in kg, and Height is in cm

The units of PDR is %/hour

3. The maximum rate at which metabolism occurs results in a peak value of the breath test called DOB_{Peak} and PDR_{Peak} , respectively. Both occur at the same time, which is called the Peak time.

a. **DOB_{peak}** : DOB_{peak} is defined as the maximum DOB.

$$DOB_{peak} = \max (DOB_0, DOB_1, DOB_2, \dots, DOB_{24})$$

b. **PDR_{peak}**: PDR_{peak} is defined as the maximum PDR.

$$PDR_{peak} = \max (PDR_0, PDR_1, PDR_2, \dots, PDR_{24})$$

4. The area under the DOB curve will be calculated for each time point. This area represents the cumulative DOB (cDOB) at any given time point.
 - a. **DOB_{x_min} and cDOB_{x_min}**: The following steps will be followed to obtain the DOB and cDOB at 5 minutes intervals (e.g. 5, 10, 15,...,60 min), where 'x' is 05, 10, 15, ..., 60 respectively. For each 'x' the following steps shall be followed:

Meridian Bioscience Israel Ltd.	Last update: May 05, 2021
SAP for Protocol BMS-EX-0118: Companion protocol for the ¹³ C-Methacetin Breath Test (MBT) for use in Bristol-Myers Squibb phase 2b studies for BMS-986036 (PEG-FGF21), under Protocols MB130-068 and MB130-069	Document Version: 1.0
Document Nº: CSD00114	Page 20 of 21

b. Find 'a', the index for which:

$$T_{a-1} < x \leq T_a$$

c. Calculate **DOB_{x_min}** using the following formula:

$$DOB_{x_min} = DOB_{a-1} + \frac{DOB_a - DOB_{a-1}}{T_a - T_{a-1}} \cdot (x - T_{a-1})$$

d. Calculate **cDOB_{x_min}** using the following formula:

$$cDOB_{x_min} = \sum_{i=1}^{a-1} \left(\frac{\frac{T_i - T_{i-1}}{60} \cdot (DOB_i + DOB_{i-1})}{2} \right) + \frac{\frac{x - T_{a-1}}{60} \cdot (DOB_{x_min} + DOB_{a-1})}{2}$$

MBT parameters results that do not have data points for at least 'x' minutes cannot be calculated

5. The PDR as well as the area under the PDR curve will be calculated for each time point. This area represents the cumulative PDR (cPDR) at any given time point in units of %.

a. **PDR_{x_min} and cPDR_{x_min}:** The following steps will be followed to obtain the PDR and cPDR at 5 minutes intervals (e.g. 5, 10, 15,...,60 min), where 'x' is 05, 10, 15, ..., 60 respectively. For each 'x' the following steps shall be followed:

b. Find 'a', the index for which:

$$T_{a-1} < x \leq T_a$$

c. Calculate **PDR_{x_min}** using the following formula:

$$PDR_{x_min} = PDR_{a-1} + \frac{PDR_a - PDR_{a-1}}{T_a - T_{a-1}} \cdot (x - T_{a-1})$$

d. Calculate **cPDR_{x_min}** using the following formula:

$$cPDR_{x_min} = \sum_{i=1}^{a-1} \left(\frac{\frac{T_i - T_{i-1}}{60} \cdot (PDR_i + PDR_{i-1})}{2} \right) + \frac{\frac{x - T_{a-1}}{60} \cdot (PDR_{x_min} + PDR_{a-1})}{2}$$

MBT parameters results that do not have data points for at least 'n' minutes cannot be calculated

Meridian Bioscience Israel Ltd.	Last update: May 05, 2021
SAP for Protocol BMS-EX-0118: Companion protocol for the ¹³C-Methacetin Breath Test (MBT) for use in Bristol-Myers Squibb phase 2b studies for BMS-986036 (PEG-FGF21), under Protocols MB130-068 and MB130-069	Document Version: 1.0
Document Nº: CSD00114	Page 21 of 21

6. The cDOB and cPDR at the peak time are called cDOB_{peak} and cPDR_{peak}, respectively. They are calculated as described in steps 4 and 5, respectively, while 'x' is the actual time 'T' of the observed peak value. The cPDR_{peak} divided by Peak time is named cPDRpeak_div_Peaktime.
7. The following list of MBT result parameters will thus be used in the statistical analysis:
 DOB_{peak}, cDOB_{peak}, PDR_{peak}, cPDR_{peak}, cPDRpeak_div_Peaktime, Time to Peak,
 DOB_{5_min}, DOB_{10_min}, DOB_{15_min}, DOB_{20_min}, DOB_{25_min}, DOB_{30_min}, DOB_{35_min},
 DOB_{40_min}, DOB_{45_min}, DOB_{50_min}, DOB_{55_min}, DOB_{60_min}, cDOB_{5_min}, cDOB_{10_min},
 cDOB_{15_min}, cDOB_{20_min}, cDOB_{25_min}, cDOB_{30_min}, cDOB_{35_min}, cDOB_{40_min},
 cDOB_{45_min}, cDOB_{50_min}, cDOB_{55_min}, cDOB_{60_min}, PDR_{5_min}, PDR_{10_min}, PDR_{15_min},
 PDR_{20_min}, PDR_{25_min}, PDR_{30_min}, PDR_{35_min}, PDR_{40_min}, PDR_{45_min}, PDR_{50_min},
 PDR_{55_min}, PDR_{60_min}, cPDR_{5_min}, cPDR_{10_min}, cPDR_{15_min}, cPDR_{20_min}, cPDR_{25_min},
 cPDR_{30_min}, cPDR_{35_min}, cPDR_{40_min}, cPDR_{45_min}, cPDR_{50_min}, cPDR_{55_min}, cPDR_{60_min}.

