Only trained personnel will perform the breath test procedure. The actual breath collection is automatically performed by the device and is not operator dependent. If the IDcircuit (a nasal cannula manufactured specifically for Exalenz) is not connected properly to the subject (e.g. the breath does not reach the device), the BreathID® MCS device will prompt the operator to adjust the IDcircuit.

1. Turn on the device from the switch in the rear and allow up to 1 hour for warm-up to complete. To perform the test, ensure that the BreathID® MCS screen shows that the device is in 'Ready' state.
2. The IDcircuit will be attached to the BreathID® MCS device and to the patient. Pressing the "Start" button on the device will begin the collection of the patient's baseline exhaled breath. This will take approximately 5-10 minutes.
3. The ¹³C-Methacetin solution is poured into a disposable cup and administrated to the patient when prompted by the device. The solution should be administered by a medical practitioner registered on the delegation log or a research nurse if specific training for administration has been given. Immediately after ingestion, the operator will press the "Continue" button, which activates the actual measurement. CO₂ production with ¹³C may be visible within a few minutes in cases with relatively functional livers.

| | |
|---|---|
| Exalenz Bioscience Ltd. | Last update: February 20, 2018 |
| Study Title: Companion protocol for the ¹³C-Methacetin Breath Test (MBT) for use in Bristol-Myers Squibb phase 2b studies for BMS-986036 (PEG-FGF21), under Protocols MB130-068 and MB130-069 | Protocol: BMS-EX-0118 Version: 1.0 |
| Document No: CSP000002 | Page 35 of 38 |

Note: In rare cases, the administration of fluids may cause vomiting. If this happens, the test should be aborted and repeated on one of the subsequent days. The experienced adverse event should be reported in the appropriate CRF section.

4. The patient should remain in a seated position breathing in a normal manner for up to 85 minutes, while data is collected.
5. The BreathID® MCS device continuously measures and analyzes the patient's exhaled breath in real time. As the ¹³C-Methacetin is metabolized, the value of the ¹³CO₂/¹²CO₂ ratio in the exhaled breath will change and will be calculated in real time by the device.

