7 ANALYSIS SETS

7.1 *Safety Analysis Set (SA)*

The Safety Analysis set will include all subjects enrolled under BMS' MB130-068 and MB130-069 studies that initiated at least one MBT (had taken the ¹³C-Methacetin solution), even if the MBT was not completed or the result was not valid.

7.2 *Efficacy Analysis Set (EA)*

The Efficacy Analysis set will include all subjects enrolled under BMS' MB130-068 and MB130-069 studies who have successfully performed the MBT test and did not have any major protocol deviations for the current study.

7.3 *Modified Efficacy Analysis Set (mEA)*

The modified Efficacy Analysis set will include all subjects enrolled under BMS' MB130-068 and MB130-069 studies who have successfully performed the MBT test. Visit specific major protocol deviation will be excluded, while keeping subjects in this analysis set for other valid visits.

Safety analyses will be performed on the SA set and efficacy analyses on the mEA set. Sensitivity analysis will be performed on the SA (corresponding to ITT) and EA set.

Meridian Bioscience Israel Ltd.	Last update: May 05, 2021
SAP for Protocol BMS-EX-0118: Companion protocol for the ¹³C-Methacetin Breath Test (MBT) for use in Bristol-Myers Squibb phase 2b studies for BMS-986036 (PEG-FGF21), under Protocols MB130-068 and MB130-069	Document Version: 1.0
Document Nº: CSD00114	Page 15 of 21

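### PDRpeak has no minimum or common recording window, so a test stopped before its peak can give a falsely low value in the SA sensitivity analysis, although cPDR30 is protected

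*SAP*

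**What the plan says.** **Peak parameters.** SAP Appendix A item 3b states that PDRpeak "is defined as the maximum PDR". The formula takes the maximum over readings indexed 0 to 24. On the source of the readings, the appendix says that "all available DOB measures with corresponding time point (T) will be retrieved from the completed eCRFs". Readings are "automatically measured every 2-3 minutes, resulting in approximately 23 DOB's and corresponding time points over one hour".

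**Timed parameters.** For values at a set time, item 4 ends with a rule: "MBT parameters results that do not have data points for at least 'x' minutes cannot be calculated". Item 5 repeats it for PDR and cPDR, writing 'n' in place of 'x'. Item 3 has no such rule. Item 6 derives cDOBpeak and cPDRpeak by setting x to the time of the observed peak.

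**Use.** SAP 8.4.1 makes PDRpeak and cPDR30 the primary responder parameters at Weeks 24 and 48 in the mEA set; any increase is a response. SAP 8.4.2.1 classifies risk by PDRpeak alone, with 20 %/h or less as high risk.

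**Analysis sets.** The SA set in SAP 7.1 keeps subjects "even if the MBT was not completed or the result was not valid". After assigning efficacy analyses to mEA, SAP 7.3 adds: "Sensitivity analysis will be performed on the SA (corresponding to ITT) and EA set".

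**Recording time.** Protocol 7.7.9 gives 60-85 minutes. Protocol 10.2 gives an upper limit: "The patient should remain in a seated position breathing in a normal manner for up to 85 minutes, while data is collected".

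**The concern.** A maximum over readings can only stay the same or fall when late readings are lost. If recording stops while the curve is still rising, the last reading becomes the peak. The plan guards cPDR30 against short recordings but not PDRpeak, so the two primary parameters treat the same incomplete test differently.

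The direction of the error depends on which test was short:

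- A short follow-up test lowers the later value and can turn a response into a non-response.
- A short Day 1 test lowers the baseline and can turn a non-response into a response. In the Cox model it can also place a subject in the high-risk group.

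The responder rule counts any increase, however small, so a modest loss can be enough to change a classification.

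**Working it through.** **1. The plan's own reading rate.** One reading every 2-3 minutes gives 60/3 = 20 to 60/2 = 30 readings per hour. The stated figure of about 23 implies 60/23 = 2.61 minutes between readings, so it is consistent.

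**2. Does index 24 define a time window?** Twenty-four intervals span 24 × 2 = 48 to 24 × 3 = 72 minutes (24 × 2.61 = 62.6 at the implied rate). A test of 85 minutes gives 85/3 = 28 to 85/2 = 42 readings. The index range therefore fixes neither a minimum time nor a common one.

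**3. Can the timed-parameter rule be borrowed?** No. In item 6, x is the time of the observed peak, and data always reach the observed peak. The rule is met automatically, however short the test.

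**4. What happens to a short test, set by set?** Suppose a test ends before 30 minutes and before its true peak.

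| | cPDR30 | PDRpeak |
|---|---|---|
| Appendix A as written | not calculated | highest reading so far |
| SA sensitivity analysis | missing | can enter, possibly too low |
| mEA analysis | missing | enters only if the test counts as successfully performed, a term with no recording time attached |

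**5. Illustration of size.** The documents give no curve shape and no time to peak. Assume PDR(t) = P × (t/tp) × exp(1 − t/tp), with P the true peak and tp its time. If recording stops at s < tp, the fraction of the true peak observed is f = (s/tp) × exp(1 − s/tp); if s ≥ tp, f = 1. For a stop at s = 10 minutes (unrounded f used throughout):

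| tp (min) | f | True peak 25 reads | True rise 25 to 27, short follow-up: 27f − 25 | True fall 25 to 23, short Day 1: 23 − 25f |
|---|---|---|---|---|
| 10 | 1.000 | 25.0 | +2.0 | −2.0 |
| 15 | 0.930 | 23.3 | +0.1 | −0.3 |
| 20 | 0.824 | 20.6 | −2.7 | +2.4 |
| 30 | 0.649 | 16.2 | −7.5 | +6.8 |
| 40 | 0.529 | 13.2 | −10.7 | +9.8 |

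Response status reverses for tp = 20, 30 and 40. The high-risk cut is reached only for tp = 30 and 40. In general the observed fraction must fall to 20/25 = 0.80 for a true peak of 25 %/h, or 20/30 = 0.67 for a true peak of 30 %/h.

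Later stops do less. At s = 20 there is no loss for tp up to 20. For tp = 30, 40 and 45, f is 0.930, 0.824 and 0.775, so a true peak of 25 reads 23.3, 20.6 and 19.4 %/h. At s = 35, where cPDR30 exists, tp = 60 gives f = 0.885: 25 reads 22.1 %/h, and only true peaks above 20 and up to 20/0.885 = 22.6 would reach the cut.

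**6. Weight of one subject.** The SAP expects fewer than 80 subjects with valid baseline and post-treatment tests. If these split equally over four arms, there are fewer than 20 per arm, and one changed classification moves an arm's responder rate by more than 1/20 = 5 percentage points. The SA denominators may be somewhat larger.

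**The case against.** The best defence is that the main analysis already has filters. The mEA set takes only subjects with a successfully performed test and drops visits with major deviations. Protocol 10.2 has tests stopped for vomiting or device malfunction terminated, recorded on a form and, if possible, repeated on a later day. SAP 8.2 takes the latest Day 1 value as baseline, so a repeat replaces an aborted test. SAP 8.3 tabulates reasons for lacking a valid test. Protocol 7.7.9 states a nominal duration, and the device signals completion. This largely stands. What remains is that neither successful performance nor validity is tied to a recording time. Protocol 10.2 lists only two termination triggers, and loss of breath signal brings only a warning on the screen.

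It can also be said that the SA set defines subjects, not values, and that SAP 5.1 leaves out subjects without MBT results. That is fair, but an incomplete test does have readings, and nothing tells the programmer to discard their maximum. Index 24 may well be mere notation for a one-hour test; it still sets no time condition.

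A reader might infer that aborted tests are routinely read as high risk or non-response in the primary analysis. The filters above do not support that. A reader might also infer that slow metabolisers peak late and so lose most. Protocol 3.2 links advanced disease to low values but says nothing about late peaks.

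**Conclusion.** The gap is real and confined. As written, Appendix A withholds cPDR30 from a test that stops before 30 minutes but still returns a PDRpeak for it, and the SA sensitivity analysis keeps the subjects concerned. The mEA analysis is exposed only if a shortened test passes as successfully performed, which the documents neither say nor exclude.

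Harm needs recording to stop before the true peak. A false high-risk label further needs the value to fall to 20 %/h or less; a false response status needs the loss to outweigh the true change. The figures above show direction and plausibility, not expected size: they rest on an assumed curve and assumed times to peak, and the documents do not say how often tests are cut short. All analyses are descriptive, which limits the consequence. The change is still worth making, because it is cheap and makes the two primary parameters consistent.

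**What to change.** In SAP Appendix A item 3:

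- Take DOBpeak and PDRpeak over one common window at every visit, defined by time and not by index 24. The nominal hour already used in Appendix A is a natural example and matches the lower end of the range in Protocol 7.7.9. The documents do not establish it as the necessary threshold, so the choice should be stated.
- Set both peaks, and the parameters derived from them (cDOBpeak, cPDRpeak, its ratio to peak time, and Time to Peak), to missing when the recording does not cover the window.
- Allow a tolerance of one reading interval, 2-3 minutes. With a 60-minute window, a last reading at or after 60 − 3 = 57 minutes would count at the wider tolerance. Without this, a complete one-hour test whose last reading falls just short of 60 minutes would lose its peak.

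In SAP 7.3, state that terminated or invalid tests contribute no PDRpeak value to the SA efficacy sensitivity analysis. The window rule also closes the mEA gap for this parameter.

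The cost is a few lines of text and one programming condition. SAP section 2 allows amendment before the sponsor accesses the data. A few shortened tests lose PDRpeak, including some whose peak may already have passed; their cPDR30 stays usable if they reached 30 minutes. Readings after the window would no longer count towards the peak.
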